## Statistical analysis plan for KetMo, NCT 05422001

Aarhus. September 15th 2023

The following plan for data analysis was decided upon at a meeting with all members of the steering committee on September 15th, 2023. The plan was made before A and B lists were obtained from the hospital pharmacy.

This study will be undertaken as an equivalence trial with the application of intention to treat analysis.

Missing data are assumed to be missing at random, no imputations.

In brief:

A study enrollment flow diagram in accordance with the CONSORT (Consolidated Standards of Reporting Trials) will be prepared. Patient characteristics and outcome measures will be reported as means, standard deviations (SDs), medians, interquartile ranges (IQRs), and percentages, as appropriate.

Primary outcome will be comparing average change of NRS at 10 minutes between the intervention and control group and analyzed using appropriate test depending on distribution. Primary outcome includes initial analysis of all included patients (n=116) and sub-analysis in two groups (prior opioid use / no prior opioid use). Appropriate test according to potential difference in NRS at T0 in the two groups (prior opioid use) will be applied for comparing the differences in NRS between the two groups.

NRS will be reported as median (interquartile range) and compared between groups at the various times using the Mann–Whitney U test. If normal distributed a multilevel mixed effects linear regression will be carried out.

Categorical data (number of patients with Ramsay Sedation Scale Level 2, any adverse events during observation) are reported as numbers (%) with 95% confidence intervals and compared using the  $\chi^2$  test. Analysis of other secondary outcomes will be dichotomized and presented for relevant time points,  $\chi^2$  test.

Secondary outcome concerning Rescue opioid will be evaluated as time to event (opioid) – non parametric – Kaplan Meier estimate will be considered, if appropriate. Alternative rescue opioid yes/no – binary regression if assumptions are fulfilled.

All P-values will be two-sided, and those below 0.05 considered significant.

Detailed statistical plan are written, printed, signed and stored in Trial Master File

[name]

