## 1.2.5 Side effects reported following anesthetic doses

The side effects reported below are all related to doses and administration pace. They are reported after ketamine is used in anesthetic doses, and thus much larger doses than in this study.

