## Frequency:

Very common: >10 %

Common: >1 % and <10 %

Not common: >0.1 % and <1 %

Rare: >0.01 % and <0.1 %

Very rare: <0.01 %

Not known (can't be estimated from available data)

Immune system disorders	
Rare	Anaphylaxis.
Neuropsychological manifestations	
Common	Emergence reactions (post-operative delirium)  vivid dream, nightmares, dizziness and restlessness, hallucnations  .
Frequency unknown	Dysphoria, anxiety, disorientation
Nervous system	
Not common	Enhanced muscle tone and spasms (resembling a partial motor or generalized motor seizure).
Eyes	
Common	Blurred vision
Not common	Diplopia, increased intraocular pressure, nystagmus
Heart	
Common	Transient tachycardia, elevated blood pressure and heart frequency
Rare	Arrhythmia, bradycardia
Vascular system	
Rare	Hypotension (when used in circulatory collapse)
Airways, thorax and mediastinum	
Common	Increased vascular resistance in the lung
	circulation, increased mucus secretion, increased

	need of oxygen, laryngospasm, transient respiratory depression*
Abdominal	. , .
Common	Nausea, vomiting, hypersalivation
Hepatobiliary dysfunction	
Frequency unknown	Abnormal test of liver function
	Drug induced liver injury**
Skin and subcutaneous tissue disorders	
Not common	Transient erythema and/or morbilliform rash,
	reactions at the injection site (pain and
	reddening)

- 1. When S-ketamine is used as single agent for anesthesia, up to 30 % of the patients are observed to have side effect in the recovery phase.
- 2. Frequency of these side effects can be reduced significantly by using a benzodiazepine.
- \*Large doses and rapid rate of administration

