## 2.5 TRIAL PROCEDURES

## 2.5.1 Patients

The trial procedures will be limited to the interventions given with the first dose of morphine (see section 2.3)

Data will be obtained from the study specific eCRF and from the electronic medical records.

 $T_0$  defined as when the ED physician/nurse evaluates NRS and the PI gives the study medication.

The trial and observation period is  $T_0$  - 120 min.

	T 0	10 min	20 min	30 min	45 min	60 min	120 min
NRS	Х	х	Х	Х	Х	Х	х

Patient rated		Х					Х
pain relief*							
Vital	Χ	Х	Х	Χ	Х	Χ	Х
parameters							
Patient		х		Х			х
reported side							
effects**							
Physician							х
reported side							
effects***							
Provider							x
satisfaction							
score****							
Patient							x
satisfaction							
score							
RASS****	 	Х	Х	Х	Х	Х	Х

\*Patients will be asked to rate their pain relief on a 6-point scale ("worse pain," "no," "little," "moderate," "good," or "complete pain relief").

In addition, patients are encouraged to spontaneously report any other side effects/adverse advent. The timing of onset and resolution of all adverse effects during the observation period will be recorded.

- \*\*\*Physician-reported side effects: nystagmus, hypertension, respiratory depression, bradycardia, hallucinations.
- \*\*\*\*Provider satisfaction with pain control will be recorded on the 4-point Likert scale with 0 being "completely unsatisfied" and 3 being "very satisfied.
- \*\*\*\*\*Richmond Agitation-Sedation Scale (RASS) will be used to evaluate agitation or sedation. (appendix 2)

TRIAGE and TOKS (tidlig opsporing af kritisk sygdom) according to the standard at AUH will be used to evaluate differences in vital parameters.

\*\*Patient-Reported Side effects: nausea, lightheadedness or dizziness, disorientation, euphoria, itching, tinnitus, double vision, abnormal dreaming or hallucinations.

There will be no questionnaires for the participants to answer, they will be asked verbally and their answers will be entered in RedCap.

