#### 3.2 Inclusion criteria

PI will screen ED patients at ED admission for the following inclusion criteria:

- 1. Emergency Department admission
- 2. Age  $\geq$  18 years and
- 3. A painful condition (NRS  $\geq$  5)
- 4. Stable vital signs defined as systolic blood pressure ≥ 90 mmHg, heart rate between 50 and 150 per minute, respiratory rate between 8 and 30 per minute, oxygen saturation greater than or equal to 92%.

Further subcategorized into

1. Prior use of opioids (daily for one week before admission)

2. No prior use of opioids (daily for one week before admission)

These broad inclusion criteria are chosen to investigate the effect of LDK in the entire, broad population with pain in the ED and the subcategorization to investigate whether LDK leads to a larger reduction on NRS in the group of patients with a prior use of opioids than those without a prior use of opioids.

We will strive to enroll participants as soon as they fulfill the criteria in the ED.

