**Exclusion criteria** 

Opioids given before study medication (i.e. in ambulance)

Date and time consent for data collection is obtained

Patient demographics and characteristics

Unique patient identifier (CPR number)

Age

Sex

Height

Weight Medications prior to enrollment Prior opioid use, dose, duration Reason for prior opioid use (cancer/non-cancer pain, postoperative, addiction) Cancer/non-cancer Site of pain/injury: Fracture/orthopedic Abdominal/flank Groin pain Postoperative pain Other/unknown Prior to randomization: Vital parameters NRS At 10, 20, 30, 45 60 and 120 min after randomization: NRS

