**RASS** 

Need for rescue morphine and total use of morphine

Physician reported side effects: nystagmus, hypertension, respiratory depression, bradycardia, arrhythmia.

TOKS and triage values as standard procedures

Patient-reported side effects: nausea, lightheadedness or dizziness, dry mouth, disorientation, euphoria, itching, tinnitus, double vision, abnormal dreaming or hallucinations.

Patient satisfaction. To be able to compare with other and future studies "no pain" and "worst pain imaginable" are chosen as anchors.

Provider satisfaction with pain control will be recorded on the 4-point Likert scale with 0 being "completely unsatisfied" and 3 being "very satisfied.

Protocol violation.

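### Vital parameters are recorded at seven times, but the public plan specifies no between-arm comparison of blood pressure or heart rate

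*Combined protocol and SAP*

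**What the plan says.** The schedule table in protocol section 2.5.1 marks vital parameters at T0, 10, 20, 30, 45, 60 and 120 min. NRS is the only other item marked at all seven times. The text below the table says that TRIAGE and TOKS, applied as is standard at the hospital, "will be used to evaluate differences in vital parameters". It does not say which summary or comparison this means.

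The variable overview in section 6.2.2 reads "Prior to randomization: Vital parameters NRS At 10, 20, 30, 45 60 and 120 min after randomization: NRS". Its list for the later times goes on to "TOKS and triage values as standard procedures" and does not name vital parameters again.

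Haemodynamic events also appear among the side effects. Section 2.5.1 has "Physician-reported side effects: nystagmus, hypertension, respiratory depression, bradycardia, hallucinations", marked at 120 min only. Section 6.2.2 gives a similar physician list with arrhythmia in place of hallucinations. Neither the physician list nor the patient list contains tachycardia in either section.

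Side effects are a secondary outcome (section 4.2.1); vital signs, TOKS and triage are not. The SAP reports any adverse events during observation as numbers and percentages with 95% confidence intervals and a chi-square test. For the rest it states: "Analysis of other secondary outcomes will be dichotomized and presented for relevant time points". Neither the SAP nor protocol sections 5.1 and 5.2 mention blood pressure, heart rate, TOKS or triage.

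**The concern.** The objective in section 2.1.5 covers safety as well as efficacy, and the last hypothesis in section 2.1.2 is that side-effect frequency is similar in the two arms. Section 1.2.5 lists "Transient tachycardia, elevated blood pressure and heart frequency" as common, although at anesthetic doses. Section 3.3 excludes patients with systolic pressure of 180 mmHg or more and several cardiac conditions. Blood pressure and heart rate are therefore natural safety measures for this comparison.

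The plan collects a dense early series of these readings and says that differences will be evaluated, but it specifies no estimate. What it does specify is a yes/no side-effect count. That count can show an overt event that someone recognises and reports. It cannot say how large an average rise was, or bound it with a confidence interval. The trial could support its statement on similar side effects and still be unable to say what haemodynamic change its own readings exclude.

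**Working it through.** **Plan's own figures.** The protocol states no precision or power for vital signs, so there is none to reproduce. Its only sample-size figure, 39 per arm in section 5.1, concerns NRS. It does reproduce: for a difference of 1.5, SD 2, two-sided 5% and 90% power, the t-test needs 38.35, so 39 per arm. It has no bearing on this point.

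**Routes by which a haemodynamic effect could reach the results**

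| Route | What the documents give | What is missing |
|---|---|---|
| Scheduled vital parameters | Seven times (2.5.1) | Any between-arm analysis |
| TRIAGE/TOKS | Stated as the means of evaluation (2.5.1); on the variable overview (6.2.2) | Thresholds, summary, comparison, place in the SAP |
| Physician-reported hypertension, bradycardia, arrhythmia | Side effects are a secondary outcome; the SAP tests adverse events by chi-square | Numeric definitions; any scheduled report before 120 min |
| Tachycardia | Could enter as arrhythmia, as a spontaneous report or through TRIAGE/TOKS | Not named on the physician or patient list |

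**Illustration of what yes/no counting costs.** From the documents: n = 116 (SAP) and two-sided 5%. Assumed: an even split (58 per arm), a true difference of 8 mmHg in systolic pressure at one time point, normal readings with SD 20 mmHg, and control means of 130, 140 or 150 mmHg. The 180 mmHg cut is borrowed from the exclusion criterion and the 160 mmHg cut is arbitrary; neither is a TOKS threshold.

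Continuous, unadjusted:
- SE = 20 × √(2/58) = 3.71 mmHg.
- Noncentrality = 8/3.71 = 2.15 on 114 degrees of freedom; critical t = 1.98.
- Power = 57%; 95% CI half-width = 1.98 × 3.71 = 7.4 mmHg.

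Single cut: the control proportion is 1 − Φ((cut − mean)/20). The ketamine proportion uses mean + 8. Power is by exact enumeration of the uncorrected chi-square test.

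| Cut (mmHg) | Control mean (mmHg) | Control vs ketamine above the cut | Power |
|---|---|---|---|
| 180 | 130 | 0.6% vs 1.8% | 1% |
| 180 | 140 | 2.3% vs 5.5% | 12% |
| 180 | 150 | 6.7% vs 13.6% | 23% |
| 160 | 130 | 6.7% vs 13.6% | 23% |
| 160 | 140 | 15.9% vs 27.4% | 34% (33.5%) |
| 160 | 150 | 30.9% vs 46.0% | 38% |

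Both analyses use SD 20, so the contrast does not depend on baseline adjustment. If the SD of the change from T0 were 15 or 10 mmHg, power would be 81% or 99%. Against a reading SD of 20, however, those values imply correlations between T0 and follow-up of 1 − 15²/(2 × 20²) = 0.72 and 1 − 10²/(2 × 20²) = 0.88. That gain would come from using T0, not from avoiding a cut.

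**Free of units.** With 58 per arm, a shift of 0.5 SD gives power 0.76 for means. For the share above a threshold that 5%, 10% or 20% of controls exceed, it gives 0.30, 0.41 or 0.51. For 0.75 SD the figures are 0.98 against 0.62, 0.77 or 0.86. A moderate shift is easily missed by a count; a large one would often show.

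**The case against.** A reader might infer that a real haemodynamic effect would go unreported, or that similarity of side effects would be concluded without a test. The documents do not support either reading. Hypertension and bradycardia are named side effects, arrhythmia is named in section 6.2.2, and section 2.5.1 records onset and resolution of all adverse effects during observation. The SAP compares adverse events by chi-square. The hypothesis concerns the frequency of side effects, and a comparison of frequencies does address it.

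Other points on that side also stand:
- The list in section 1.2.5 concerns anesthetic doses, and it says: "The side effects reported below are all related to doses and administration pace". Nothing says that vital signs are scheduled in order to watch for this effect, and its size at the trial dose is unknown.
- The schedule row does not name blood pressure or heart rate; they are inferred from the stable-vital-signs definition in section 3.2. That TRIAGE and TOKS band or pool readings is also inference, because the local guideline is not in the documents.
- Section 6.2.1 calls the variable list a brief overview and leaves details to the data dictionary. Its silence on later vital parameters does not show that the raw readings are unavailable.
- The public SAP describes itself as brief and refers to a detailed plan in the Trial Master File, which cannot be checked here.
- Vital signs are not a listed secondary outcome, so the SAP's dichotomising sentence does not clearly reach them. The single-cut calculation illustrates yes/no reporting; it is not a test that the plan specifies.

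These points limit the claim to the public text and to moderate or transient shifts. They do not supply a between-arm estimate.

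**Conclusion.** The point holds in a limited form. On the public documents, the stated evaluation of the scheduled vital parameters is by TRIAGE/TOKS alone, and no between-arm comparison of blood pressure or heart rate is specified. Overt events have a yes/no route into the results. A moderate or short-lived change would not be estimated, and tachycardia has no named place among the side effects.

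The size is illustrative only. Under the assumptions above (8 mmHg, SD 20, 58 per arm), power is 57% for the comparison of means and about 1% to 38% for one cut. Other SDs, effects or thresholds would move these figures. What does not depend on them is that a mean difference with its confidence interval uses information that an event count discards. This is a cheap improvement to safety reporting; it does not affect the primary analysis.

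**What to change.** In protocol section 2.5.1 and in the SAP, supplement the TRIAGE/TOKS evaluation with the following:

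1. For systolic pressure and heart rate, the ketamine-minus-placebo difference in change from T0 at the early scheduled times (for example 10, 20 and 30 min), adjusted for the T0 value, with 95% confidence intervals.
2. The maximum rise in each over 120 min, summarised by arm.
3. Respiratory rate and oxygen saturation summarised by arm, using each patient's minimum.
4. TRIAGE and TOKS values by arm, as a descriptive supplement.

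Confirm that the raw readings at every scheduled time are in the data dictionary. If the detailed plan in the Trial Master File already contains such an analysis, making that text public is enough.

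The cost is some wording and one safety table. No new measurement, patient or change to clinical care is needed. The downside is a few extra safety estimates without multiplicity control, so they should be presented as estimates with intervals and not as confirmatory tests.

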## 2.5.2 Clinical personnel

Prior to the beginning of patient enrollment and continuously throughout the enrollment period, the clinical teams involved in the treatment of patients at the participating hospital will be informed about the background and objectives of the trial, the inclusion/exclusion criteria, the interventions, and the trial procedures they are involved in. We anticipate, in-person didactics monthly with informal sessions.

Provider Satisfaction Score will be used after the observation period is over (120 min after study medication is injected) to evaluate provider's clinical satisfaction with the treatment. Provider satisfaction with pain control will be recorded on the 4-point Likert scale with 0 being "completely unsatisfied" and 3 being "very satisfied. There will be no questionnaires for the provider, they will be asked verbally and their answers entered in RedCap.

## 3. SETTING AND PATIENT POPULATION

#### 3.1 Setting

The trial will be conducted at the ED at Aarhus University Hospital, and may be expanded to the ED at Regional Hospital West Jutland at a later stage. (an amendment will be added in this case)

#### 3.2 Inclusion criteria

PI will screen ED patients at ED admission for the following inclusion criteria:

- 1. Emergency Department admission
- 2. Age  $\geq$  18 years and
- 3. A painful condition (NRS  $\geq$  5)
- 4. Stable vital signs defined as systolic blood pressure ≥ 90 mmHg, heart rate between 50 and 150 per minute, respiratory rate between 8 and 30 per minute, oxygen saturation greater than or equal to 92%.

Further subcategorized into

1. Prior use of opioids (daily for one week before admission)

2. No prior use of opioids (daily for one week before admission)

These broad inclusion criteria are chosen to investigate the effect of LDK in the entire, broad population with pain in the ED and the subcategorization to investigate whether LDK leads to a larger reduction on NRS in the group of patients with a prior use of opioids than those without a prior use of opioids.

We will strive to enroll participants as soon as they fulfill the criteria in the ED.

#### 3.3 Exclusion criteria

- 1) Initial management by trauma-team
- Systolic blood pressure ≥ 180 mmHg, severe untreated arrhythmia, unstable angina pectoris, recent myocardial infarction ( < 30 days), severe heart failure (Ejection fraction < 40 %)

- 3) Symptoms of untreated hyperthyroidism
- 4) Cirrhosis with ascites
- 5) Known/suspected pregnancy, or breastfeeding
- 6) Patients, for whom consent is not obtainable or psychiatric forced treatment.
- 7) Previously enrolled in the trial
- 8) Psychiatric illness prior to admission defined as prior psychosis/schizophrenia
- 9) Diagnosed untreated glaucoma
- 10) Known hypersensitivity to ketamine or to any excipient or prior use of ketamine with a negative experience (i.e. hallucinations)
- 11) Patient clearly influenced by drugs or alcohol

## 3.4 Withdrawal

Each participant has the right to withdraw from the trial at any time. In addition, the Investigator may discontinue a participant from the trial at any time if the Investigator considers it necessary for any reason including:

Ineligibility (either arising during the trial or retrospectively having been overlooked at screening)

- Significant protocol deviation
- Withdrawal of consent
- Loss to follow up

## 3.5 Co-enrollment

There will be no general restrictions on entry into other clinical trials, although this will be evaluated on a case-by-case basis. However, patients enrolled in this study will not be able to be enrolled in other acute-pain treatment projects at the time of admission in the ED and the first 120 minutes after study medicine is given.

#### 4. OUTCOMES

## 4.1 Primary outcome

#### 4.1.1 Definition

The primary outcome measurement is pain reduction assessed on NRS 10 minutes after study medication is given,  $T_0$ .

 $(T_0 = when the physician/nurse evaluates pain at administration of study medication)$ 

#### 4.1.2 Rationale

This study is powered to detect a difference in pain reduction of at least 1.5 on the NRS scale between the groups. (LDK vs placebo)

## 4.2 Secondary outcomes

## 4.2.1 Definitions

Secondary outcomes:

- Need of morphine within the 30, 60 and 120 min after administration of study medication
- Pain intensity after 20, 30, 45, 60 and 120 min
- Side effects
- Patients satisfaction Score
- Provider Satisfaction Score

 Comparison of pain reduction in the two parallel groups (prior opioid, no prior opioid) on all time intervals.

## 4.2.2 Rationale

Very few prospective studies have examined the effect of LDK as an adjunct to opioid for acute pain treatment in the ED setting. Almost none in the general patient population with pain and no one have evaluated the effect in patients having a prior use of opioids.

Increasing the efficacy of pain treatment and reducing the incidence of adverse side effects is always a desirable clinical improvement, as is the reduction of resources necessary to effectively treat pain in the ED.

Adding LDK to morphine may result in a better pain treatment for the patient and reduced need for opioids.

## 4.3 Safety and harm

#### 4.3.1 General consideration

The personal in the ED are highly trained in acute pain therapy. The PI is Specialty trainee in anesthesiology, Department of Anesthesiology AUH and she will be at trial site whenever study medicine is given. The doses used in this study are very low (0,1 mg/kg), and we do not expect any serious adverse reactions with this dose. We therefore believe it is safe for both individual patients and at the group level to be enrolled into this study after relevant inclusion and exclusion criteria.

The overall benefit and potential harm will be captured in our secondary outcomes, and the clinical team/PI will document any specific adverse reactions suspected to be related to the intervention - if there are AE or AR's after the observation period ( $T_0$ - $T_{120}$ ), the patients are observed as standard on AUH.

All participants are expected to receive opioids, but the amount is hypothesized to differ.

AE as natural consequences of the reason for hospitalization will not be registered in the eCRF. (i.e. blood transfusion).

Investigators should use their knowledge of the patient, the circumstances surrounding the event, and an evaluation of any potential alternative causes to determine whether or not an AE is considered to be related to the study drug, indicating "yes" or "no" accordingly. The following guidance will be taken into consideration:

- Temporal relationship of event onset to the initiation of study drug
- Course of the event, considering especially the effects of dose reduction, discontinuation of study drug, or reintroduction of study drug (where applicable)
- Known association of the event with the study drug or with similar treatments
- Known association of the event with the disease under study
- Presence of risk factors in the patient or use of concomitant medications
  known to increase the occurrence of the event
   Presence of non-treatment-related factors that are known to be associated
  with the occurrence of the event

